# Modification

## Basic Info

Confirmation Number:	cihghbcb
Protocol Number:	832295
Created By:	[name]
Principal Investigator:	[name]
Protocol Title:	Novel neural circuit biomarkers of major depression response to computer-augmented CBT (1R01MH110939 - 01A1)
Short Title:	CCBT fMRI R01
Protocol Description:	This is a trial of an FDA-approved treatment for MDD, computer-augmented cognitive behavioral therapy (CCBT), to examine novel potential neural circuit biomarkers of treatment response. 100 subjects total: 40 controls, 60 MDD. MDD subjects begin CCBT at the earliest scheduling availability. CCBT treatment lasts 8 wks. All subjects will have an fMRI at baseline before CCBT and a final fMRI after the treatment phase. Those beginning CCBT later will complete an additional fMRI before CCBT.
Submission Type:	Biomedical Research
Application Type:	EXPEDITED Category 3 and Category 4

## PennERA Protocol Status

Approved

### Resubmission\*

No

### Are you submitting a Modification to this protocol?\*

Yes

## Current Status of Study

### Study Status

Currently in Progress

*If study is currently in progress, please enter the following*

#### Number of subjects enrolled at Penn since the study was initiated

4

#### Actual enrollment at participating centers

0

*If study is closed to further enrollment, please enter the following*

#### Number of subjects in therapy or intervention

0

**Number of subjects in long-term follow-up only**

0

**IRB Determination**

If the change represents more than minimal risk to subjects, it must be reviewed and approved by the IRB at a convened meeting. For a modification to be considered more than minimal risk, the proposed change would increase the risk of discomfort or decrease benefit. The IRB must review and approve the proposed change at a convened meeting before the change can be implemented unless the change is necessary to eliminate an immediate hazard to the research participants. In the case of a change implemented to eliminate an immediate hazard to participants, the IRB will review the change to determine that it is consistent with ensuring the participant's continued welfare. Examples: Convened Board Increase in target enrollment for investigator initiated research or potential Phase I research Expanding inclusion or removing exclusion criteria where the new population may be at increased risk Revised risk information with active participants Minor risk revisions that may affect a subject's willingness to continue to participate Expedited Review Increase in target enrollment at Penn where overall enrollment target is not exceeded or potentially sponsored research Expanding inclusion or removing exclusion where the new population has the same expected risk as the previous, based on similarities of condition Revised risk information with subjects in long-term follow-up Minor risk revisions with no subjects enrolled to date

Expedited Review

**Modification Summary**

Please describe any required modification to the protocol. If you are using this form to submit an exception or report a deviation, enter 'N/A' in the box below.

Modifying study procedures to include an additional 15 minute computer task. Informed consent forms have been modified to include information about this computer task. Two key study personnel have been added to the study.

**Risk / Benefit**

Does this amendment alter the Risk/Benefit profile of the study?

No

**Change in Consent**

Has there been a change in the consent documents?

Yes

**If YES, please choose from the options below regarding re-consenting**

Our site does not plan to obtain re-consent

## Deviations

**Are you reporting a deviation to this protocol?\***

No

## Exceptions

**Are you reporting an exception to this protocol?\***

No

# Protocol Details

## Resubmission\*

Yes

#### **Responsible Org (Department/School/Division):**

10579 - PS-Center for the Neuroscience of Depression & Stress

**Disclosure of Significant Financial Interests\***

Does any person who is responsible for the design, conduct, or reporting of this research protocol have a **FINANCIAL INTEREST**?

No

**Penn Intellectual Property\***

To the best of the Principal Investigator's knowledge, does this protocol involve the testing, development or evaluation of a drug, device, product, or other type of intellectual property (IP) that is owned by or assigned to the University of Pennsylvania?

No

**Certification**

I have reviewed the *Financial Disclosure and Presumptively Prohibited Conflicts for Faculty Participating in Clinical Trials* and the *Financial Disclosure Policy for Research and Sponsored Projects* with all persons who are responsible for the design, conduct, or reporting of this research; and all required Disclosures have been attached to this application.

Yes

## Biomedical Research

**Clinical Trial\***

Is this a clinical trial?

Yes

If Yes, please be aware that for each clinical trial conducted or supported by a Federal department or agency, one IRB-approved informed consent form used to enroll subjects must be posted by the awardee or the Federal department or agency component conducting the trial on a publicly available Federal Web site that will be established as a repository for such informed consent forms.

**Investigator Initiated Trial\***

Is this an investigator initiated trial?

No

**Drugs or Devices\***

Does this research study involve Drugs or Devices?

No

**IND Exemption**

**For studies that fall under an IND exemption, please provide the number below**

**For studies including IND or IDE's, please provide the number(s) below**

**IDE Review\***

NOTE: For research involving investigational devices, you are required to review the guidance on Managing Research Device Inventory. Consult the Penn Manual for Clinical Research: [https://www.med.upenn.edu/pennmanual/secure/investigational-product-management-at-sites-not-using-investigational-drug-services-\(ids\).html](https://www.med.upenn.edu/pennmanual/secure/investigational-product-management-at-sites-not-using-investigational-drug-services-(ids).html) Please check the box Yes if you have reviewed the guidance.

Yes

**Research Device Management\***

Please indicate how research device(s) will be managed.

Not Applicable (no investigational devices)

**Drug, Herbal Product or Other Chemical Element Management \***

Please indicate how drugs, herbal products or other chemical entities will be managed.

Not Applicable (no drugs, herbal products or other chemical entities)

**Radiation Exposure\***

Are research subjects receiving any radiation exposure (e.g. X-rays, CT, Fluoroscopy, DEXA, pQCT, FDG, Tc-99m, etc.) that they would not receive if they were not enrolled in this protocol?

No

**Gene Transfer\***

Does this research involve gene transfer (including all vectors) to human subjects?

No

**Human Source Material\***

Does this research include collection or use of human source material (i.e., human blood, blood products, tissues or body fluids)?

Yes

**CACTIS and CT Studies\***

Does the research involve Center for Advanced Computed Tomography Imaging Services (CACTIS) and CT studies that research subjects would not receive if they were not part of this protocol?

No

**CAMRIS and MRI Studies\***

Does the research involve Center for Advanced Magnetic Resonance Imaging and Spectroscopy (CAMRIS) and MRI studies that research subjects would not receive if they were not part of this protocol?

Yes

**Investigational Agent or Device within the Operating Room\***

Does the research project involve the use of an investigational agent or device within the Operating Room?

No

**Cancer Related research not being conducted by an NCI cooperative group\***

Does this protocol involve cancer-related studies in any of the following categories?

No

**Processing of Materials\***

Will the research involve processing (such as over encapsulating, or compounding)?

No

**In-House Manufacturing of Materials\***

Will the research involve processing (such as over encapsulating, or compounding)?

No

**Medical Information Disclosure\***

Does the research proposal involve the use and disclosure of research subject's medical information for research purposes?

Yes

**If the answer is YES, indicate which items is is provided with this submission:**

Modified research informed consent document that incorporates HIPAA requirements

**CTRC Resources\***

Does the research involve CTRC resources?

No

**Pathology and Laboratory Medicine Resources\***

Will samples be collected by hospital phlebotomy and/or processed or analyzed by any of the clinical laboratories of the University of Pennsylvania Health System?

No

**Research Involves Apheresis, Cell Collection, and/or Blood Product Collection\***

Does this research involve collection of blood products in the Penn Donor Center and/or the use of apheresis for treatment or collection of cells or other blood components?

No

**Research involving blood transfusion or drug infusions\***

Will your research involve blood transfusion or infusion of study drug in 3 Ravdin Apheresis Unit for research purposes?

No

**Trial in Radiation Oncology**

Is this research a prospective trial being done in Radiation Oncology, and if so, has this protocol been approved by the Radiation Oncology Protocol committee?

N/A

**Study in Radiation Oncology**

Is this research a retrospective study being done in Radiation Oncology, and if so, has this project been reviewed by the Radiation Oncology Clinical Research Group?

N/A

**Use of UPHS services\***

Does your study require the use of University of Pennsylvania Health System (UPHS) services, tests or procedures\*, whether considered routine care or strictly for research purposes?

No

**Primary Focus\***

Sociobehavioral (i.e. observational or interventional)

**Protocol Interventions**

- Sociobehavioral (i.e. cognitive or behavioral therapy)**
  - Drug**
  - Device - therapeutic**
  - Device - diagnostic (assessing a device for sensitivity or specificity in disease diagnosis)**
  - Surgical**
  - Diagnostic test/procedure (research-related diagnostic test or procedure)**
  - Obtaining human tissue for basic research or biospecimen bank**
  - Survey instrument**
  - None of the above**

**The following documents are currently attached to this item:**

*There are no documents attached for this item.*

**Department budget code**

000 - 000 - 0 - 000000 - 0000 - 0000 - 0000

## Funding Sponsors

Name:	NATIONAL INSTITUTE OF MENTAL HEALTH/NIH/DHHS
Type:	UPENN Federal

### Funding sponsors billing address

If you have selected a commercial or industry sponsor, please provide the appropriate address and contact information for the Sponsor for the purposes of billing for IRB review fees (initial review, continuing review and convened modification fees apply here). If the Sponsor is not industry/commercial, this information is not necessary to provide with your application.

### Funding sponsors gift

Is this research being funded by a philanthropic gift?

No

### Regulatory Sponsor

#### IND Sponsor

none

000 - 000 - 0 - 000000 - 0000 - 0000 - 0000

#### Industry Sponsor

None

### Project Funding\*

Is this project funded by or associated with a grant or contract?

Yes

### Selected Proposals

Proposal No	Title
10058145	Novel neural circuit biomarkers of depression response to computer-augmented CBT

### Sponsor Funding

Is this study funded by an industry sponsor?

No

### Status of contract

### The following documents are currently attached to this item:

*There are no documents attached for this item.*

## Multi-Center Research

### Penn as lead

1. Is this a multi-center study where Penn is serving as the Lead Site or the Penn PI is serving as the Lead Investigator?

No

### Management of Information for Multi-Center Research

### Penn irb of record

2. Is this a multi-center study where the Penn IRB will be asked to serve as the IRB of Record for other external study sites?

No

## ***Other Sites***

No other sites

# **Protocol**

### **Abstract**

This is a trial of an FDA-approved treatment for Major Depressive Disorder (MDD), computer-augmented cognitive behavioral therapy (CCBT), to examine novel potential neural circuit biomarkers of treatment response rather than to test efficacy. We will enroll 60 subjects, 18-60 years, who are seeking treatment for a current episode of Major Depressive Disorder. We also will enroll 40 healthy controls of a similar age/sex distribution. MDD subjects will be scheduled to receive CCBT at the first available appointment; all will be scheduled within 4 weeks. All subjects will have an fMRI at baseline; MDD subjects will have an fMRI after treatment. MDD subjects scheduled to start CCBT treatment after 3 weeks will complete an additional fMRI before they begin CCBT.

### ***Objectives***

#### **Overall objectives**

The overall objectives of the study are to examine novel potential neural circuit bio-markers of treatment response to computer-augmented cognitive behavioral therapy (CCBT) for people with MDD. Aim 1: Compare baseline resting state functional connectivity and task-induced activity between MDD and controls: Hypothesis 1a): Compared with controls, depressed participants will have disruptions in resting state functional connectivity in the amygdala-cognitive-executive (C-E) network and the amygdala-default mode network (DMN); and 1b) will have decreased emotional conflict task-induced activation in rostral/dorsal anterior cingulate cortex (ACC), dorsal lateral prefrontal cortex (DLPFC), and inferior frontal gyrus (IFG). Aim 2: Assess CCBT treatment effects on resting state functional connectivity and task induced activity in MDD comparing post-CCBT treatment to pre-CCBT treatment. Hypothesis 2a) Compared with pre-CCBT neuroimaging measures, following active treatment there will be increase in C-E connectivity and decreased amygdala-DMN connectivity. 2b) These changes will be correlated with symptom reduction and 2c) increases in rostral/dorsal ACC, DLPFC and IFG activation during the emotional conflict task. Exploratory Aim: 1a) Predict the effects of baseline brain measures on treatment outcomes. Hypothesis: Using clinical decision-support algorithms, clinical outcome trajectories and differential response to treatment will be predicted from baseline data (brain connectivity, task-based activity and cortical thickness). 1b) Predict the effects of baseline executive function on treatment outcomes. Hypothesis: Using clinical decision-support algorithms, clinical outcome trajectories and differential response to treatment will be predicted from baseline executive function data. Developing such algorithms to help determine risk trajectories is important for more effective treatment assignment. Secondary Aims: Data collected from actigraphy, saliva sample, and remote monitoring via the Beivei cellphone application will be used as preliminary evidence examining the effects of sleep-wake patterns, microbiome, and total physical activity on treatment outcomes in individuals experiencing depression.

#### **Primary outcome variable(s)**

Aim 1: 1a) resting state functional connectivity 1b) emotional conflict task-induced brain activity Aim 2 Treatment effects: 2a) amygdala-connectivity 2b) changes rostral/dorsal ACC, DLPFC and IFC activation during the emotional conflict task. Patients will serve as their own controls pre-post treatment. In addition, patients who wait longer for treatment (3-4 weeks) will be compared in a second scan with those who receive immediate treatment (1-2 weeks).

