## Characteristics of the Study Population

### **Target population**

60 participants with Major Depressive Disorder, in current MD episode of at least moderate severity, as indicated by the SCID-5 and MADRS (greater than or equal to 20). There will be 40 healthy control participants of similar age/sex. Combining with subjects from protocol 826910, we will enroll 37 additional MDD participants and 24 additional healthy controls through protocol 832295 to meet the overall target of 100 subjects (60 MDD, 40 Healthy controls).

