which we will also conduct for comparison. Aim 1b: To assess baseline differences between MDD and HC in Emotional Conflict task-induced activation in the dorsal ACC, DLPFC, and IFC, we will apply two approaches: First, perform the voxel-wise general linear model to detect group differences on the AHIF-AHIN contrast; Secondly, we will conduct brain-wide fPCR to explore variations that are associated with depression symptoms while controlling the anxiety symptoms. All analyses will be adjusted for age and sex, and corrected for multiple comparisons by controlling the false discovery rate. Aim 2: Aim 2a: To assess the effect of CCBT on the functional connectome, we will test for differences in amygdala-connectivity between MDD patients who receive treatment immediately (within 1-2 weeks of screening) and those who receive treatment later (within 3-4 weeks of screening). We will examine deficits identified in Aim 1 to compare the MDD groups treated immediately (1-2 weeks) vs. treated later (3-4 weeks) for changes in these regions, adjusting for motion, age and gender. We will also conduct a whole-brain feature search through structured functional principal component analysis (SFPCA) [87]. SFPCA incorporates the longitudinal design complexity and models variation in amygdala-connectivity induced by CCBT through dimension-reduced principal components that are associated with longitudinal changes. Instead of generating contrasts for each hypothesis, it utilizes all available data by explicitly modeling the correlation structures among the observed connectivity maps. Aim 2b: To assess changes of the conflict task-induced activity in ACC, DLPFC, and IFC, we will use the same techniques of SFPCA and targeted mixed-effects modeling adjusting for age and sex. We will also investigate the correlation between the patterns of treatment-induced connectivity and activation normalization. Further, we will investigate the dose-response relationship between total time engaged in CCBT and changes in brain connectivity and activity. Exploratory Aim: We will first use PCR to predict treatment response after CCBT using the baseline amygdala-connectivity map. To avoid overfitting, we will evaluate the prediction performance using bootstrapped cross-validation by iteratively applying learning predictive patterns to 90% of the subjects and testing on the remaining 10%. We will assess treatment response using continuous score changes in depression and anxiety, and remission status (defined by MADRS10 after CCBT). For continuous measures of response, we will assess predicted mean-square error (MSE) for symptomatic change in two ways: first, we will simply estimate the predictive performance of the principal scores. Next, we will compare a predictive model based on regression with only baseline depression scores to a model with both baseline scores and principal scores to assess the added value of the imaging markers. For remission status, we will assess both the predictive performance of the principal scores and the added value of these markers above baseline depression scores and other demographics (age, sex, socio-economic status) using receiver-operator characteristic (ROC) curve analysis. Differences in the performance will be assessed by building confidence intervals for increased area under the curve (AUC) using bootstrapped cross-validation. We will apply the same techniques to the contrast of parameter maps from the conflict task, as well as to the cortical thickness maps. We will build second stage meta-classifiers that integrate the patterns found using these functional and structural imaging measures using generalized linear modeling, which will allow us to integrate the imaging predictors with age, sex, and other demographic information. To assess the importance of baseline executive function measures, we will examine the improvement in predictive performance by including these into the meta-classifiers. Other machine learning algorithms such as support vector machines and random forests, as well as collaborative learning will also be explored to achieve optimal performance. We will also assess the amount of model improvement by incorporating joint resting-state, task-based activation, and cortical thickness patterns into the previous PCR model by calculating c-statistics and prediction indices (such as net reclassification improvement and integrated discrimination improvement etc.) sequentially. Finally, we will investigate sparse patterns of association between imaging measures and depression phenotypic measures using sparse canonical correlation analysis. \*\*\*NOTE REGARDING DATA ANALYSIS WITH PROTOCOL 826910\*\*\* Procedures and data elements are the same between #826910 and #832295, therefore they will not need to be reconciled. The data from the two study will be added together. Participant data from the Immediate CCBT group from #826910 and the early CCBT group from #832295 will be grouped together for analysis. Participant data from the Wait-list Followed by CCBT group from #826910 and the delayed CCBT group in #832295 will be grouped together for analysis.

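### The Aim 2 second-scan contrast sets a treated interval of about 8-11 weeks against an untreated one of 2-4 weeks with no stated elapsed-time term, so it does not isolate the CCBT effect

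*Combined protocol and SAP*

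**What the plan says.** Primary outcome variable(s) gives two Aim 2 comparisons. Patients act as their own controls before and after treatment, and in addition "patients who wait longer for treatment (3-4 weeks) will be compared in a second scan with those who receive immediate treatment (1-2 weeks").

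The Analysis Plan, Aim 2a, reads the between-group comparison causally: "To assess the effect of CCBT on the functional connectome, we will test for differences in amygdala-connectivity between MDD patients who receive treatment immediately" and those treated later. Regions identified in Aim 1 are compared between the groups "for changes in these regions, adjusting for motion, age and gender". A whole-brain search is added, described in these words: "SFPCA incorporates the longitudinal design complexity and models variation in amygdala-connectivity induced by CCBT through dimension-reduced principal components". For Aim 2b, "we will use the same techniques of SFPCA and targeted mixed-effects modeling adjusting for age and sex". Neither paragraph names scan interval or elapsed time as a model term.

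The power analysis (C.10.1, under Accrual) bases its Aim 2 connectivity statement on 30 treated patients against untreated data from the Later group, and calls the result treatment effects.

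The timing comes from Design and Procedures. Early patients start CCBT within 2 weeks of the first scan, treatment lasts 8 weeks, and the final scan is in CCBT Week 9. Later patients have an untreated second scan 2 to 4 weeks after the first.

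**The concern.** A delayed-start control removes spontaneous change only for as long as the control group is observed untreated. Here the treated group is observed for much longer than the untreated group, and the two windows do not overlap. Whatever happens without treatment between about week 3 and about week 10 appears in the Early change and has no counterpart in the Later change. The pre-post comparison does not help, because it has no concurrent control for that period either.

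This matters because Aim 2 is a primary aim of a mechanistic trial, and the expected message is that CCBT changed the circuits. Depressive episodes can remit without treatment; Potential Study Risks itself calls the effects of spontaneous remission considerable. If connectivity follows mood, some of the reported circuit change could be natural recovery.

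**Working it through.** **Inputs.** Early wait 0-2 weeks and treatment 8 weeks (Design); final scan in CCBT Week 9, taken as 8-9 weeks after the start (Procedures); Later untreated scan at 2-4 weeks (Procedures); IFC-amygdala change 0.09 with SD 0.05, precuneus-amygdala change 0.08 with SD 0.04, 30 Early patients and 80% power (C.10.1). Assumed, because the plan does not say: 30 in the Later group, the SD is that of the change, and one two-sided 0.05 test.

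**1. The plan's own figure.** SE of the contrast = SD × √(2/30).
- IFC: 0.05 × 0.2582 = 0.0129, and 0.09/0.0129 = 6.97.
- Precuneus: 0.04 × 0.2582 = 0.0103, and 0.08/0.0103 = 7.75.

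Power exceeds 99.9% for both, so 80% holds only as a lower bound. The point does not depend on it.

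**2. Intervals.**
- Early: 0 + 8 = 8 weeks to 2 + 9 = 11 weeks, midpoint 9.5.
- Later: 2 to 4 weeks, midpoint 3.
- Time without a comparator: 8 − 4 = 4 weeks to 11 − 2 = 9 weeks, midpoint 6.5.

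Other sections place the Later start or its extra scan after 3 weeks, or at 3-4 weeks (Abstract, Primary outcome variable(s), C.10.1, Analysis Plan). The passages should be reconciled, but the gap stays at 4 weeks or more under each.

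**3. Share of linear drift left in the contrast** = 1 − (Later interval / Early interval).
- 8 against 4 weeks: 1 − 4/8 = 50%.
- 11 against 2 weeks: 1 − 2/11 = 82%.
- Midpoints: 1 − 3/9.5 = 68%.

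**4. Illustration with no CCBT effect.** Let drift over 9.5 weeks be a fraction f of 0.09. Bias = f × 0.09/9.5 × gap. Rejection rate = P(|Z + bias/0.0129| > 1.96).

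| f | Bias, gap 4 to 9 weeks | False positives, gap 4 / 6.5 / 9 weeks |
|---|---|---|
| 10% | 0.004 to 0.009 | 6% / 8% / 10% |
| 25% | 0.009 to 0.021 | 11% / 22% / 38% |
| 50% | 0.019 to 0.043 | 31% / 67% / 91% |

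For precuneus-amygdala, with f applied to 0.08, the ranges are 6-11%, 13-45% and 37-96%.

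**5. Can the Later group reveal the drift?** The 95% half-width of its untreated change is 2.045 × 0.05/√30 = 0.019. At the mid-window gap, drift of 0.0013 per week gives 10% false positives and 0.0039 per week gives 50%. Over 3 weeks these rates amount to 0.0039 and 0.0117, and the Later group's interval would exclude zero in only about 7% and 24% of trials.

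**6. Would an elapsed-time term solve it?** Take participant intercepts, residual SD 0.05/√2, Early scans at 0 and 9.5 weeks, Later scans at 0, 3 and 11.5 weeks, a post-CCBT indicator and linear weeks. The SE is 0.030 and power for 0.09 is about 85%. That model assumes no repeat-scan effect. Adding a repeat-scan indicator raises the SE to 0.052 and cuts power to about 40%. Time and treatment are too closely aligned in this design for a time term to be a reliable remedy.

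**The case against.** The strongest case on the other side has five parts.

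- **The randomised wait does real work.** This stands. It controls for repeat scanning and for early spontaneous change. A reader might infer that the contrast has no control value; the documents do not support that.
- **SFPCA may handle time.** It uses all available scans and is described as longitudinal, and how it treats scan time rests on a cited source that is not in the documents. A reader might infer that all natural recovery after the first weeks will be credited to CCBT. That is too strong: it could be, because no term is stated. Two further analyses bear on specificity: "we will investigate the dose-response relationship between total time engaged in CCBT and changes in brain connectivity and activity", and the correlation of circuit change with symptom reduction (Overall objectives). Neither adjusts the randomised contrast.
- **The false-positive rates may not describe the planned test.** Under Aim 1b the Analysis Plan says that all analyses will be corrected by false discovery rate. If that extends to Aim 2, the rates above apply only before correction.
- **Part of the sample comes from another protocol.** The plan states that "we will enroll 37 additional MDD participants and 24 additional healthy controls through protocol 832295", so 60 − 37 = 23 MDD participants come from 826910, whose delayed arm was a wait-list. Their scan interval is not given. The plan does say "Procedures and data elements are the same between #826910 and #832295, therefore they will not need to be reconciled", which supports assuming the same intervals but does not prove it.
- **The short wait is a design limit, and rewording removes no bias.** True. The remedy changes what may be concluded, not the data.

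A reader might also infer that Potential Study Risks promises full separation of spontaneous remission from CCBT in this trial. That sentence is a general remark about delayed-treatment studies and need not change.

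**Conclusion.** The point holds in limited form. The second-scan contrast estimates CCBT plus about 4-9 weeks of elapsed time that no comparator covers, and the plan attributes it to CCBT. The pre-post change has no concurrent control for that period. Under linear drift, 50-82% of the spontaneous change would remain in the contrast. The actual bias is unknown, because the documents give no drift rate; the false-positive figures show sensitivity to assumed drift and are not predictions.

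The conclusion rests on three assumptions: the Week 9 scan falls 8-9 weeks after the start of CCBT, the participants from 826910 follow the same intervals, and SFPCA contains no unstated adjustment for scan time. The false-positive figures also assume linear drift, 30 per group, an SD of change of 0.05 and a single uncorrected test. This should be fixed: the data remain useful, but the stated interpretation goes further than the design allows.

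**What to change.** 1. In Primary outcome variable(s), C.10.1 and Analysis Plan Aim 2, state the unequal scan intervals (about 8-11 against 2-4 weeks). Define the second-scan contrast and the pre-post change as CCBT plus uncontrolled elapsed time, not as CCBT net of time.
2. Report the Later group's untreated change from scan 1 to scan 2, with its 95% confidence interval, beside the contrast. State in advance that an interval including zero is not evidence of no drift.
3. Leave out an elapsed-time model, or include it only as a sensitivity analysis labelled as assuming linear drift and no repeat-scan effect. It should not replace the planned contrast, and its precision should not be presented without the repeat-scan result (SE 0.052, power about 40%).

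Items 1 and 2 cost some wording and one reported interval from scans already planned, with no new scans and no schedule change. The downside is a weaker stated conclusion, and a Later-group interval (about ±0.019) too wide to rule out drift that matters. Item 3, if kept, needs the actual scan dates.
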